5.3 Post-treatment Evaluations

- History and focused physical exam at 6 weeks, 3 months and then every 6 months for 2.0-2.25 years after completion of RT and then at the discretion of the treating physician until 5-5.25 years after the completion of RT. (Zubrod performance status; Karnofsky or ECOG performance status may be used to estimate Zubrod).
- Blood work in relation to RT:
 - PSA at 6 weeks, 3 months and then every 6 months for 5.25 years.
 - Testosterone at 6 weeks, 3 months and 9 months. If testosterone remains abnormally low, tests will continue to be done at each follow-up visit.
 - Liver function tests at 6 weeks and 3 months.

- Lipid profile at 6 weeks, 3 months and 9 months and within 2 months of 2 yr. prostate post-treatment biopsy.
- Plasma and serum (up to 4 tubes), and urine (approximately 50 mL) for Research Fluid tests will be at 3 months and then within 2 months prior to 2 yr. prostate post-treatment biopsy, if possible.
- Multiparametric functional MRI's with timed contrast at 3 and 9 months, and within 2 months prior to the 2 yr. post-treatment prostate biopsy.
- Prostate biopsy at 2 – 2.5 years post completion of all therapy (2 yr. post-treatment biopsy). For this biopsy procedure, 12-14 biopsies are recommended with cores taken from sextant regions plus the bilateral lateral base, bilateral lateral mid-prostate, and bilateral lateral apex. At least 2-3 of these biopsies should be from suspicious/Previously positive areas. The bilateral transition zone may be biopsied as well. Fewer biopsies may be obtained at the discretion of the urologist. The post-treatment biopsy will also be done, if possible, using the Eigen Artemis® system software for MRI-ultrasound fusion (see sections 1.2 and 3.3.4) that is in beta testing. The Eigen Artemis system fusion software (FDA approved) may be used to fine-tune the location of the tumor and biopsies by fusion of the previously obtained multiparametric MRI to the transrectal ultrasound in real time. The ultrasound is the true guidance imaging parameter that identifies the prostate boundaries and other nearby structures. The MRI is fused to the ultrasound such that the biopsies may be directed to a region in the ultrasound space. The patient will be informed of the results.
- Bone scan at the discretion of treating physician based on clinical suspicion of metastasis.
- Psychosocial questionnaires follow-up at 6 weeks, 3 months, 9 months, 15 months and yearly to 5.25 years.

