 - The Expanded Prostate Cancer Index Composite Questionnaire-SF12 (EPIC-SF12).
 - Memorial Anxiety Scale for Prostate Cancer patients (MAX-PC).
- International Prostate Symptom Score (IPSS) will be done at each follow-up visit for 5.25 years. This includes 6 weeks, 3 months and every 6 months thereafter RT.

Note: Measurements and follow-up visits should occur \pm 2 weeks up to the 3 month visit and \pm 4 weeks for subsequent measurements/visits.

If for whatever reason the patient is unable to return for follow up (e.g. insurance problems, moving out of town, etc.) we will continue to follow the patient via phone call and we will try to get their records from any outside facility.

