9.1 Definitions

- *Biopsy failure rate*: The proportion of positive biopsy findings among patients without clinical or biochemical failure 2-2.5 years after completing study treatment (RT or ADT, whichever is longer).
- *Two-year failure rate*: The proportion of patients with either (i) biopsy failure 2-2.5 year after completing treatment (RT or ADT, whichever is longer) or (ii) evidence of biochemical and/or clinical failure (local, regional or distant failure) at any time prior to the planned 2 year post treatment biopsy.
- *Acute toxicity*: toxicity occurring during treatment and within three months of completing treatment
- *Late toxicity*: toxicity occurring more than three months after treatment completion.
- *Failure rate*: The cumulative incidence of biochemical or clinical failure allowing for competing risk as needed. Clinical failure is defined as at least local failure due to newly identified extension outside of the prostate after initial regression, or urinary obstructive symptoms with carcinoma found at TURP or regional/distant failure due to radiographic evidence metastasis (nodal or hematogenous spread). Biochemical failure is defined as $PSA \geq \text{nadir} + 2 \text{ ng/mL}$
- *Failure-free Survival (FFS)*: The elapsed time from start of radiotherapy to first documented evidence of biochemical or clinical failure or death from any cause, whichever occurs first. In the absence of any event defining failure, follow-up time will be censored at the date of last documented failure-free status.

- *Overall Survival (OS)*: The elapsed time from start of radiotherapy to death from any cause. For surviving patients, follow-up will be censored at the date of last contact.
- *Biomarker expression*: Quantification of the amount of the biomarker specific immunohistochemical staining in the area of tumor
- *QOL*: Two contemporary instruments will be utilized to assess patient function and bother (Expanded Prostate Cancer Index Composite-SF12 (EPIC-SF12) and the prostate cancer-specific anxiety Memorial Anxiety Scale for Prostate Cancer patients (MAX-PC).

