Time to event endpoints will be analyzed by Kaplan-Meier (KM) or competing risk (CR) methods as indicated in the Table 14.5 (80, 77) Where the Kaplan Meier method is used, point estimates and 2-sided 95% confidence intervals will be reported for selected times such as 1, 2

and 5 years from treatment start using Greenwood's variance and the log-log transform method. Median event-free or overall survival time, if attained, will also be reported. Treatment arms will be compared by the log rank test. Cox regression models including treatment as a covariate will be used to explore the prognostic effect of baseline characteristics as well as biomarkers and proteomic and genomic profiles. Regression findings will be expressed as hazard ratios and corresponding 95% confidence intervals. For analyses involving competing risks, cumulative incidence rates will be reported for selected times with corresponding 2-sided 95% confidence intervals based on the variance estimator of Aalen and the log-log transform method. Treatment comparison of event rates will be based on Gray's test and regression models investigating prognostic factors will be fit by the method of Fine and Gray. (78, 81) Where study data indicate that at most a small number of competing risk events have occurred, analysis will be simplified by treating such events as censored observations in a Kaplan Meier analysis, since the resulting overestimation of the event rate will be negligible.

Table 14.5. Time-to-event endpoints.

Endpoint	Analysis	Events (earliest)	Competing risks	Censoring
Failure rate	CR	CF, BF, BF+ CF (within 6 months of each other) Start subsequent therapy Death related to prca without prior evidence of failure	Death unrelated to prca	Last clinical +PSA assessment
Toxicity rate (to be done separately for GI and GU)	CR	Onset of grade 2+ and 3+ toxicity	Start subsequent therapy Death, any cause	Last contact
Failure free survival (FFS)	KM	CF, BF, BF+ CF Start subsequent therapy Death, any cause	n/a	Last clinical or PSA assessment
Prostate cancer mortality	CR	Death related to prca	Death unrelated to prca	Last contact
Overall survival (OS)	KM	Death, any cause	n/a	Last contact

KM: Kaplan-Meier. **CR:** competing risk. **BF:** Biochemical failure. **CF:** clinical failure. **prca:** prostate cancer. **GI:** gastrointestinal. **GU:** genitourinary.

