APPENDIX I
STUDY CALENDAR

Assessment	Prior to RT	Weekly during RT	Follow-up					Other
			During Last Week of RT	6 Weeks after RT	3 Mo after RT	Every 6 months thereafter up to 2-2.25 years post-end of all treatment	FU until 5-5.25 years (At the discretion of the physician)	
History & Physical Exam*	X	X	X	X	X	X	X	
Functional-MRI of prostate/pelvis ^a	X				X			At 9 mo., and within 2 mo. of 2 yr. prostate biopsy
Bone Scan ^b	X							As needed
Prostate protocol biopsy ^c	X							2 – 2.5 years post completion of all therapy (2 yr. biopsy)
Prostate fiducial markers ^c	X							
CT and MRI simulation	X							
PSA ^a	X		X	X	X	X	X	
Serum-Testosterone ^d	X		X	X	X			At 9 months after RT
Liver function tests ^a	X		X	X	X			
Complete blood cell counts ^a	X		X		X			
Lipid Profile ^a	X		X	X	X			At 9 months and within 2 mo. prior to 2 yr. prostate biopsy
EPIC-SF-12, MAX-PC ^e	X		X	X	X			At 9 months, 15 mo. and yearly to 5.25 years
IPSS ^f	X		X	X	X	X	X	At each follow-up visit
ADT ^g	X							
Plasma and serum, and urine collection for research ^h	X		X		X			Within 2 mo. prior to 2 yr. prostate biopsy

*Toxicity will be assessed at each scheduled history and physical exam visit. Interval history will be obtained during and following RT at these visits. History and physical within 8 weeks prior to protocol entry.

(a)Obtained \leq 3 months of enrollment.

(b)Obtained \leq 4 months of enrollment if PSA >15 ng/mL or Gleason score ≥ 8 disease. For all others, to be obtained at the discretion of the treating physician.

- (c) The initial protocol prostate biopsy is optional per the patient's desire, as indicated on the consent, and will be carried out during fiducial marker placement, if applicable. In follow-up, prostate biopsy will be obtained at the first sign of local failure or a rising PSA, or at 2-2.5 years after treatment (after radiotherapy or androgen deprivation – whichever is longer) if there is no evidence of failure. The second biopsy is not optional (the patient must agree), but the biopsy may be refused later or may not be performed due to a medical contraindication.

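### Table 14.5 censors the failure rate and failure-free survival by different rules; if the failure-rate rule requires an exam and a PSA together, the five-year failure rate can be biased upward

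*Combined protocol and SAP*

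**What the plan says.** Table 14.5 (Section 14.5) lists the time-to-event endpoints. The failure rate is a competing-risk analysis censored at "Last clinical +PSA assessment". Failure-free survival (FFS) is a Kaplan-Meier analysis censored at "Last clinical or PSA assessment". Both rows count clinical failure, biochemical failure and start of subsequent therapy. No reason is given for the different censoring.

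Section 9.1 says of FFS that "follow-up time will be censored at the date of last documented failure-free status". It gives no censoring rule for the failure rate. It defines biochemical failure from PSA alone (nadir + 2 ng/mL).

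The follow-up passages do not fully agree:
- Section 5.3 schedules the history and physical exam to about 2 to 2.25 years after radiotherapy, "and then at the discretion of the treating physician until 5-5.25 years after the completion of RT".
- Section 5.3 schedules "PSA at 6 weeks, 3 months and then every 6 months for 5.25 years".
- The study calendar (Appendix I) marks both the exam and the PSA in one late column, headed "FU until 5-5.25 years (At the discretion of the physician").
- Section 5.3 also says that "International Prostate Symptom Score (IPSS) will be done at each follow-up visit for 5.25 years", and Appendix IV expects a six-monthly follow-up form over the same period. Both imply that visits continue.

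**The concern.** Under one reading of the failure-rate row, event-free time and events are measured on different clocks. A failure can be recorded from PSA alone at any scheduled draw up to 5.25 years. An event-free man is credited with follow-up only to his last date with both a clinical assessment and a PSA. If his exams stop at about 2.25 years, he leaves the risk set then, even though later PSA values show no failure. A man in the same position whose PSA rises at year 4 stays in and counts as an event at year 4. Section 9.2.2 adds a work-up for a rising PSA, so men who fail are also the ones more likely to be assessed clinically.

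Censoring then depends on outcome. The late risk set is too small and the estimated failure rate too high. At stake are the five-year failure rate and the analysis at the end of Section 14.5 that restarts the clock at the two-year biopsy, because most of that follow-up lies in the discretionary period.

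**Working it through.** **The plan's own figures.** The plan states no expected five-year failure rate, so there is none to reproduce. Its one design calculation, 80% power with 36 men per arm (52.5% against 22.5%, one-sided Fisher's exact test at 5%), reproduces at 80.3% by full enumeration. It concerns the two-year proportion and is not touched by this point.

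**Inputs from the documents.** PSA every 6 months to 5.25 years and scheduled exams to 2.25 years (Section 5.3); about 5% biochemical or clinical failure within two years (Section 14.2).

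**Assumptions.** A constant failure hazard λ. A share q of men has no clinical assessment after 2.25 years. The plus sign means both assessments. Failures found later by PSA alone are counted. Deaths and the gap between PSA draws are ignored in the closed form.

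**Hazard.** From 5% at two years, λ = −ln(0.95)/2 = 0.0256, about 2.6% a year. A hazard of 4% a year is a second, assumed value; it implies 1 − exp(−0.08) = 7.7% at two years, above the plan's figure.

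**Formula.** Let S(t) = exp(−λt). After 2.25 years the observed risk set is S(t) − c, with c = q·S(5.25), because the men removed are those without exams who never fail during follow-up. Integrating the inflated hazard from 2.25 to 5 years gives

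estimated failure at 5 years = 1 − S(2.25) × [S(5) − c] / [S(2.25) − c].

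**With λ = 0.0256:** S(2.25) = 0.9439, S(5) = 0.8796, S(5.25) = 0.8740. At q = 0.5, c = 0.4370 and the estimate is 1 − 0.9439 × 0.4426/0.5069 = 17.6%. The true value is 1 − 0.8796 = 12.0%.

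**With λ = 0.04:** S(2.25) = 0.9139, S(5) = 0.8187, S(5.25) = 0.8106. At q = 0.5, c = 0.4053 and the estimate is 1 − 0.9139 × 0.4134/0.5086 = 25.7%. The true value is 18.1%.

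| Share without late exams (q) | Estimate, 2.6% a year (true 12.0%) | Estimate, 4% a year (true 18.1%) |
|---|---|---|
| 0% | 12.0% | 18.1% |
| 30% | 14.5% | 21.6% |
| 50% | 17.6% | 25.7% |

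**Check with competing deaths and discrete PSA visits.** A simulation of 200,000 men per scenario estimated cumulative incidence at 5.25 years, with 5% failure by 2.25 years, unrelated death at 1% a year (assumed), and net failure by 5.25 years varied from 10% to 30% (assumed). The overstatement was about 1 to 5 points at q = 25%, 4 to 13 at q = 50% and 11 to 28 at q = 75%, and nil at q = 0.

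**The condition that matters most.** In the same simulation, with 20% net failure and q = 50%, leaving out failures after the last joint assessment gave 19.2% against 19.3%. The bias almost disappears and only follow-up is lost: event-free men average 0.5 × 5.25 + 0.5 × 2.25 = 3.75 years instead of 5.25.

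**Post-biopsy analysis.** Starting the clock at 2.25 years as an approximation, with q = 0.5, failure to year 5 is estimated at 1 − 0.4134/0.5086 = 18.7% against a true 1 − 0.8187/0.9139 = 10.4% at 4% a year, and at 1 − 0.4426/0.5069 = 12.7% against 1 − 0.8796/0.9439 = 6.8% at 2.6% a year.

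**The case against.** The strongest reply is that the documents show inconsistent wording, not a demonstrated bias. Three conditions must hold together: the plus sign means both, later PSA-only failures count, and many stable men have no late clinical assessment. No document gives the last quantity. The urinary symptom score, the six-monthly follow-up form and the phone and outside-record follow-up in Section 5.3 all suggest that contact continues. Table 14.5 refers to clinical assessment in general, which need not mean a physical exam. The calendar also puts PSA under the discretionary heading, so the contrast between exams and PSA is less clean than Section 5.3 alone suggests.

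Much of this stands. It limits the size of the effect but does not remove the problem. The same table uses a plus sign for combined biochemical and clinical failure, which Section 14.5 defines as evidence of both, and the FFS row uses a different connective. Biochemical failure alone is a listed event, and nothing restricts it to dates with an exam. The first two conditions are therefore the natural reading, though not a stated one.

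A reader might infer that the FFS rule has an equal and opposite flaw, crediting a contact without PSA as free of biochemical failure. Section 9.1 partly answers this, since such a contact arguably does not document failure-free status, and with six-monthly PSA the extra time is short. A reader might also take any gap between the two endpoints as an artifact of censoring. They differ by design as well: FFS counts every death, while the failure rate treats death unrelated to prostate cancer as competing.

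**Conclusion.** The concern holds in conditional form. The plan has three wordings for censoring two closely related endpoints, and the natural reading of the failure-rate row makes censoring depend on outcome once exams become discretionary. If men skip late exams, the late failure rate is biased upward: by 5.6 points (17.6% against 12.0%) with half unexamined at the hazard implied by the plan's two-year figure, by 7.6 points (25.7% against 18.1%) at the assumed 4%, by nothing if no one skips, and by almost nothing if failures after the last joint assessment are left out.

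A reader might infer that the five-year failure rate will be overstated by a known, large amount. The documents do not support that, because the share without late exams is not given and the handling of later PSA-only failures is not stated. Nor do they support any effect on the primary result. The two-year proportion and its Fisher test fall within the period of scheduled exams, as do the one- and two-year time-to-event estimates. Only late secondary estimates are affected, including the post-biopsy analysis.

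The calculations apply the same q to both arms, so they show a bias in level. In this open-label trial, unequal late exam frequency by arm or by biopsy result could also distort comparisons, but nothing in the documents shows that it would occur.

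**What to change.** Use one censoring rule in both rows of Table 14.5: censor event-free patients at the last PSA assessment that documents failure-free status, and align the Section 9.1 wording with it. State that biochemical failure is counted from PSA alone. State how clinical failures and, for FFS, deaths after the last PSA are handled, for example counted as events, with a sensitivity analysis that censors at the last PSA. That sensitivity analysis is needed because counting such events while dropping event-free time over the same interval recreates the asymmetry on a smaller scale.

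Reconcile Section 5.3, the late column of the Appendix I calendar and the Appendix IV form schedule, so that it is clear which late assessments are scheduled and which are discretionary.

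The statistical change needs two table cells and a few sentences, and no new data. Its small cost is that event-free clinical follow-up after the last PSA is not used. It should be settled before the five-year analysis, so that the choice between readings is not made with the results in view.

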8.0 CORRELATIVE/SPECIAL STUDIES

Prior to treatment during fiducial marker placement, needle biopsy of the prostate will be performed if the patient agrees (optional). Tissue from paraffin blocks will be used for biomarker quantification and correlative studies with treatment outcome.

At 2-2.5 years after completion of treatment (radiotherapy or androgen deprivation – whichever is longer) all patients, with or without documented failure will undergo transrectal needle biopsy of the prostate, unless clinically contraindicated or the patient refuses. For this biopsy procedure, 12-14 biopsies are recommended with cores taken from sextant regions plus the bilateral lateral base, bilateral lateral mid-prostate, and bilateral lateral apex. At least 2-3 of these biopsies should be from suspicious/Previously positive areas. The bilateral transition zone may be biopsied as well. Fewer biopsies may be obtained at the discretion of the urologist. The ultrasound is the true guidance imaging parameter that identifies the prostate boundaries and other nearby structures. The MRI is fused to the ultrasound such that the biopsies may be directed to a region in the ultrasound space. These data will enable us to evaluate the extent of disease eradication, as well as the prognostic significance of positive biopsies in men who are otherwise free of evidence of disease (low PSA and palpably normal prostate gland).

The 2 yr. post-treatment biopsy is for research purposes. If the biopsies contain prostate tumor cells, the results will be discussed with the patient and additional management considerations made apart from this clinical trial. Many times tumor cells are seen on prostate biopsies at 2-2.5 yr., but the cells show radiation treatment effect. In this situation, it is reasonable to continue to follow the PSA and re-biopsy a year later to look for clearance of the tumor cells. The strategy to re-biopsy will be up to the treating physician and will not be governed by the protocol.

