Evaluable: Patients who are study eligible and receive an initial dose of radiotherapy, either SIMRT or HTIMRT will be considered *evaluable for safety*, regardless of whether or not the full course of radiation treatment is completed according to protocol. To be *evaluable for efficacy*, study eligible patients must complete radiation treatment and have follow up sufficient to include either the planned 2-year post treatment biopsy or earlier evidence of biochemical or clinical failure (within 2 years of treatment completion). These patients comprise the main analysis set.

Exclusions: Any patient who is enrolled on study but does not receive an initial dose of radiation treatment will be excluded from all efficacy analyses. Any patient who initiates treatment and is later found to be ineligible for study (e.g., protocol violation) will be withdrawn from study but will be followed for toxicity and clinical outcome; the experience of such patients will be characterized separately from that of patients who are evaluable for efficacy. Reasons for exclusion of enrolled patients from analysis of safety or efficacy will be characterized.

Study endpoints are defined in Section 9.1.

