The primary trial endpoint, two-year failure rate, will be estimated for each treatment arm as a proportion with corresponding 95% confidence interval by the exact binomial method. Comparison of the failure rate for SIMRT versus HTIMRT will be based on a one-sided Fisher's exact test at a 5% significance level. Similar estimation and comparison will be done for the biopsy failure rate among clinical/biochemical failure-free patients at the two year post RT follow up. Biopsy findings two years post RT will be further characterized as negative, atypical, carcinoma with treatment effect, or carcinoma without treatment effect and compared by treatment arm using Fisher's exact test. Biomarker and proteomic/genomic characteristics of prostate biopsy tissue obtained two-year post treatment, and changes relative to baseline, will be summarized by descriptive statistics. Change from baseline will be tested for significance using t-test (means) or McNemar's test (proportions) for paired data and comparison of changes by treatment arm will be based on two-sample tests (t-test or Fisher's exact test). (For biomarker studies, nonparametric tests or data transformations to attain approximate normal distributions will be applied as needed.) Logistic regression models adjusted for treatment will be used to investigate the association between baseline factors, including biomarkers and proteomic/genomic profiles, and biopsy failure two-years post treatment. Changes in biomarkers and proteomic/genomic characteristics will also be investigated for association with biopsy failure. (79)

Patients will be followed for disease progression and vital status for a period of five years after completing study treatment. Progression of disease will be categorized as biochemical failure (BF), clinical failure (CF), or combined (BF + CF), where combined failure refers to documented evidence of BF and CF occurring within 6 months of each other with the earlier date used. CFs will be further categorized as local, nodal, or distant. Start of subsequent therapy will be considered a failure event for selected analyses as indicated in the table below. Deaths will be categorized as related/unrelated to prostate cancer. The number of observed failures will be tabulated by treatment arm and failure type. Similarly, vital status will be tabulated by treatment arm and presence or absence of disease at last follow up.

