Finally, to assess the prognostic value of 2-year post treatment biopsy findings, we will further study patients who had this procedure without prior evidence of biochemical or clinical failure. Taking the date of biopsy as the start of follow up, we will analyze subsequent failure rates and failure-free survival and test for association with biopsy positivity and treatment arm.

QOL scores will be calculated in accordance with established scoring methods for each instrument. Descriptive summaries of scores at baseline and each subsequent follow up will include median and range, means and standard deviations. Where criteria for clinically meaningful differences have been established, we will also categorize changes in these scores (computed by subtracting baseline from subsequent score) as indicating improvement,

worsening, or no change and summarize these by counts and percentages. Comparison by treatment arm at baseline and at treatment completion will be based on t-test (average score) and Fisher's exact test (percent improved). Further analysis allowing for repeated measurement will be conducted using mixed models.

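### Section 9.1 and Table 14.5 disagree on whether subsequent therapy is a failure; under the table, the test of the 2-year biopsy's prognostic value is partly circular

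*Combined protocol and SAP*

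**What the plan says.** Section 9.1 defines the failure rate as "The cumulative incidence of biochemical or clinical failure allowing for competing risk as needed", and failure-free survival (FFS) as "The elapsed time from start of radiotherapy to first documented evidence of biochemical or clinical failure or death from any cause", whichever is first. Further treatment appears in neither. Section 14.3 makes that section the reference: "Study endpoints are defined in Section 9.1".

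Section 14.5 takes another line. The text ahead of Table 14.5 states: "Start of subsequent therapy will be considered a failure event for selected analyses as indicated in the table below". The table's FFS row gives the events as "CF, BF, BF+ CF Start subsequent therapy Death, any cause". Its failure-rate row also lists the start of subsequent therapy, and adds prostate cancer death with no earlier failure.

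Section 14.5 closes with an analysis of biopsied men who had no earlier biochemical failure (BF) or clinical failure (CF), followed from the biopsy date: "we will analyze subsequent failure rates and failure-free survival and test for association with biopsy positivity and treatment arm". These are the two endpoints with conflicting definitions, and none is named here.

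Two further passages bear on this. Section 5.3 says of the biopsy: "The patient will be informed of the results". Section 8.0 says that if tumor cells are found, "the results will be discussed with the patient and additional management considerations made apart from this clinical trial". It adds that where the cells show radiation effect, PSA surveillance with a repeat biopsy a year on is a reasonable course.

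**The concern.** A prognostic analysis asks whether the marker predicts something that happens independently of knowing the marker. Here the result is disclosed and can prompt treatment, and under Table 14.5 starting treatment is itself a failure. A positive biopsy can then produce the outcome against which it is tested. An association could appear even if positive and negative men had the same later risk of BF/CF, and a real association would look stronger than it is. Under Section 9.1 this route does not exist, because therapy is not an event.

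At stake is one of the reasons Section 8.0 gives for doing the biopsy: to learn what a positive result means in men otherwise free of disease. If only the therapy-inclusive result were reported, a reader could not separate later disease failure from a treatment decision that the biopsy prompted. With two definitions on file, the choice could also be made after the results are known.

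**Working it through.** **1. The definitions side by side.**

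| Endpoint | Section 9.1 | Table 14.5 |
|---|---|---|
| Failure rate | BF or CF | BF, CF, subsequent therapy, prostate cancer death without prior failure |
| FFS | BF, CF, death from any cause | BF, CF, subsequent therapy, death from any cause |

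Section 14.3 points to the first column and the text of 14.5 to the second. No order of precedence is stated.

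**2. The plan's design figures (Section 14.2).** The control failure rate reproduces: 0.05 + 0.95 × 0.50 = 0.525. Exact enumeration of the one-sided 5% Fisher test with 36 per arm, 52.5% v 22.5%, gives 80.3% power against the stated 80%. These figures are not in dispute; they only set the size of the analysis group.

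**3. Men in the biopsy analysis.** Assume 5% early BF/CF in both arms (the plan states this for the standard arm).
- Reaching biopsy: 36 × 0.95 = 34.2 per arm, 68.4 in all.
- Positive, SIMRT: 34.2 × 0.50 = 17.1.
- Positive, HTIMRT: (0.225 − 0.05)/0.95 = 0.184, and 34.2 × 0.184 = 6.3.
- Total: about 23 positive and 45 negative.

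**4. False association if the table governs.** These assumptions are not in the documents: BF/CF risk over 3 years after biopsy (5.25 − 2.25) is 15% in both groups; a share s of positive men starts therapy because of the biopsy, spread evenly over the first 6 months; there are no deaths. The event probability in positive men is 1 − (1 − 0.15)(1 − s). The log-rank results come from 20,000 simulated trials per cell with exponential BF/CF times. With no deaths there are no competing events, so the failure-rate and FFS comparisons coincide. Fisher's test is an exact stand-in at 23 v 45.

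| s | Event probability, positive men | Log-rank, two-sided 5% | Same, BF/CF risk 10–25% | Fisher one-sided | Fisher two-sided |
|---|---|---|---|---|---|
| 0% | 15.0% | 4.5% | 4.0–5.2% | 2.4% | 3.4% |
| 5% | 19.3% | 9.0% | 7.4–9.4% | 6.4% | 5.6% |
| 10% | 23.5% | 17.4% | 13.6–21.4% | 13.4% | 11.1% |
| 25% | 36.3% | 59.0% | 46.3–68.9% | 50.4% | 44.9% |
| 50% | 57.5% | 97.9% | 94.6–99.1% | 95.8% | 93.6% |

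The plan sets one-sided tests for arm comparisons but gives no sidedness for biopsy positivity. A separate one-sided log-rank simulation (5,000 trials per cell, 15% risk) gave about 5% at s = 0, 25% at 10%, 56% at 20% and 81% at 30%.

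**5. If a real association exists.** Suppose true BF/CF risk is 30% in positive and 15% in negative men (assumed), a ratio of 2.0.
- Therapy counted as failure: 1 − 0.70 × 0.75 = 47.5% at s = 25%, and 1 − 0.70 × 0.50 = 65% at s = 50%. The ratios are 47.5/15 = 3.2 and 65/15 = 4.3.
- Therapy as a competing event: the BF/CF hazard is −ln(0.70)/3 = 0.119 per year. The chance of BF/CF before therapy, averaged over 6 months, is about 0.029. This gives 0.75 × 0.30 + 0.25 × 0.029 = 23.2% and 0.50 × 0.30 + 0.50 × 0.029 = 16.5%. The ratios are 23.2/15 = 1.5 and 16.5/15 = 1.1.

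The first handling overstates the association and the second understates it.

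**The case against.** The strongest reply is that the plan largely says which rule governs. Section 14.5 announces that therapy counts where the table shows it, and the prognostic analysis sits in the same section. On that reading the fault is mainly a failure to update Section 9.1 and the cross-reference in 14.3. This is fair, but it makes the circular branch the likelier one.

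Second, the reach is small. The analysis is not among the objectives in Section 2, and no sample size, error rate or randomized conclusion depends on it. This stands and limits the weight of the point.

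Third, the size is hypothetical. The share of positive men treated because of the biopsy is unknown, the high percentages need 25% or 50%, and Section 8.0's observation option would lower the share. This also stands, although that option is described only for cells with treatment effect, while Section 14.5 separately recognizes carcinoma without it. Section 1.4.2 cites about 50% biochemical failure 8–10 years after a positive biopsy. At a constant hazard this is 1 − 0.5^(3/10) = 19% to 1 − 0.5^(3/8) = 23% over 3 years, which lies within the 10–25% range shown.

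Fourth, the plan expects positivity to be prognostic, so inflation matters more than false association. Step 5 shows that inflation.

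Fifth, failures will be tabulated by type. That table is by treatment arm, however, and does not show the split by biopsy result.

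**Conclusion.** The concern holds. The conflict between Section 9.1 and Table 14.5 is plain in the text and depends on no assumption. The circularity is conditional: it needs the table to govern and some positive men to start therapy because of the biopsy. The documents leave the first unsettled and give no rate for the second.

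If both conditions are met, a modest share is enough to matter. With 10% of positive men treated (about 2 of 23), the two-sided log-rank false-association rate rises from about 5% to 14–21% over assumed BF/CF risks of 10–25%. The primary two-year failure rate, its sample size and its power are unaffected. This should be corrected, but it does not threaten the trial's main result.

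**What to change.** - Reconcile Section 9.1 with Table 14.5 for the failure rate and FFS, including the prostate cancer death that only the table adds to the failure rate. State in the biopsy analysis which definition it uses.
- For the association with biopsy positivity, make BF/CF the main outcome, with death handled as each endpoint specifies. Report the therapy-inclusive version as a sensitivity analysis.
- Record the reason for any subsequent therapy.
- For therapy that precedes BF/CF, show results both with therapy as a competing event and with censoring at therapy. State that either may be biased: the first may pull the association toward the null, and censoring is informative.
- The therapy-inclusive composite may stay for the randomized arm comparison.

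The cost is plan wording, one data field and extra model runs on about 68 men. No handling of therapy is unbiased, so choosing BF/CF as the main version is partly a judgment. That is the reason to show the versions side by side.
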